#### Analysis Methods for ACEND

Parents of subjects will complete the Assessment of Caregiver Experience with Neuromuscular Disease (ACEND) questionnaire at screening on Day 183 and Day 302. This assessment instrument has been designed to quantify the caregiver impact experienced by parents of children affected with severe neuromuscular diseases, including children with SMA (Matsumoto et al. 2011).

The ACEND includes a total of seven domains assessing physical impact (including feeding/grooming/dressing, sitting/play, transfers, and mobility) and general caregiver impact (including time, emotion, and finance) and each domain comprises several items. The total score for a domain with n items, each item assessed on ordinal scale from 1 to z, is derived as follows: 100 multiplied by (Mean of the n items in the domain -1) divided by (z-1). This total score will be on a scale of 0 to 100 with a higher score indicating a greater impact on the caregiver. At least two items for the time domain and one item for the remaining domains need to be non-missing for a total to be calculated; else the total score will be set to be missing.

The baseline for ACEND is defined as the last non missing assessment prior to the first dose of study treatment.

Product: Nusinersen	Statistical Analysis Plan
Study: 232SM203	Version: 1.0

The main analysis is to compare the change from baseline for each domain at Day 302 between 50/28 mg Group and 12/12 mg Group using an ANCOVA model with treatment group as a factor and age at screening, baseline plasma NfL and baseline score as covariates. Missing data will be handled using the multiple imputation method.

#### Analysis Methods for PedsQL

Subjects will be evaluated using the Pediatric Quality of Life Inventory (PedsQLTM) Measurement 4.0 Generic Core Scales and 3.0 Neuromuscular Module (Vami et al. 1999) at screening (the baseline assessment), Day 183 and Day 302.

The questionnaires are specific to the age of the subject, and sites are instructed to get both subjects and caregivers to complete the same age specific questionnaire as was collected at baseline irrespective of whether or not the subjects cross an age boundary at a subsequent visit.

The PedsQL parent questionnaire is collected for children in the following age categories: 2-4, 5-7, 8-12. Four dimensions are collected: Physical, Emotional, Social and School functioning and each item is scored on a 5 point ordinal scale (0=Never, 1=Almost Never, 2=Sometimes, 3=Often, 4=Almost Always). The PedsQL patient questionnaire is collected for children in the following categories: 5-7, 8-12. Similar dimensions and 5-point ordinal scale are used as for the parents but for subjects aged 5-7 years a 3-point ordinal scale is collected, omitting the response levels of 1 and 3.

In the neuromuscular module, one parent questionnaire is collected for all subjects irrespective of age with three dimensions: "About my child's neuromuscular disease", "Communication" and "Family resources". The same 5-point ordinal scale is collected for each question.

The patient neuromuscular disease questionnaire is collected for subjects in the following age categories: 5-7, 8-12. The questionnaire for subjects aged 5-7 years uses the 3-point ordinal scale as above and has only one dimension – "About my Neuromuscular disease".

The questionnaires for the remaining two categories cover dimensions for "Communication" and "Family resources" and use the 5-point ordinal scale.

In scoring a dimension the first step is to reverse and linearly transform to a 0-100 scale (0=100, 1=75, 2=50, 3=25, 4=0), so higher score is indicative of a better health related quality of life. If greater than 50 percent of the items within a dimension are missing then the dimension score will not be computed, otherwise the mean score for the dimension will be calculated as the sum of items over the number of items answered.

A psychosocial health summary score, constructed from three dimensions, will be calculated as the sum of items over the number of items answered in the emotional, social and school functioning scales. A total score will be calculated as the sum of all the items over the number of items answered on all the scales. If greater than 50 percent of the items are missing, then the summary score or total score will be set to be missing.

For the neuromuscular module, a score for each dimension and then total score will be calculated in the same manner, no health summary scores are evaluated.

Product: Nusinersen	Statistical Analysis Plan
Study: 232SM203	Version: 1.0

The baseline for PedsQL is defined as the last non missing assessment prior to the first dose of study treatment.

For the generic PedsQL and neuromuscular module, the change from baseline in the total score will be presented by visit and treatment group for both the parent and subject assessments. Similarly, the changes in the individual dimensions and health summary score will also be presented.

The change from baseline score (each total score and parent/subject evaluation separately) at Day 302 50/28 mg Group and 12/12 mg Group will be analyzed using ANCOVA model with treatment group as a factor and age at screening, baseline plasma NfL and baseline score as covariates. Missing data will be handled using the multiple imputation method. The imputation will be performed separately for each dimension and total and psychosocial summary scores. Due to the age specific nature of these questionnaires, subjects aged 2-4 years would not be expected to complete the self-evaluation and if this is the case then imputations will not be performed, and the subjects will be excluded from the analysis.

# 5.1.6. Number and Length of Hospitalizations

If the number of hospitalizations during the study is greater than 5 in total then an analysis will be performed as described in the following section using the rate at which they occur, otherwise just a listing will be provided.

For descriptive purposes, the aggregate hospitalization rate will be calculated for each group by dividing the total number of hospitalizations that occurred in the group by the total number of subject-years on study.

Annualized hospitalization rate will be calculated for each subject as the number of hospitalizations that the subject experienced divided by the number of days on study and this ratio multiplied by 365. Annualized hospitalization rate will be analyzed by a negative binomial regression model, adjusted for disease duration at Baseline. The logarithmic transformation of the time on the study will be included in the model as the "offset" parameter. If the data are under dispersed, or if the negative binomial regression model does not converge, a Poisson regression model with the same covariate will be used instead of the negative binomial regression model. Dispersion will be evaluated from the Pearson chi-squared statistic.

For each subject, the total time spent in hospital during the study will be calculated and prorated according to number of days on study. Based on the prorated time in hospital, treatment groups will be compared to an ANCOVA adjusting for each subject's disease duration at Screening, age at symptom onset and baseline Plasma NfL.

# 5.1.7. Clinical Global Impression of Change (CGIC) [Physician, Caregiver] at Day 302

CGIC will be assessed at Days 29, 64, 183 and 302. The CGIC rating scale was developed as a brief standalone assessment of the clinician's view of the patient's global functioning after initiating a study medication [Guy 1976]. The CGIC provides an overall clinician-determined summary measure that takes into account all available information, including knowledge of the

Product: Nusinersen	Statistical Analysis Plan
Study: 232SM203	Version: 1.0

patient's history, psychosocial circumstances, symptoms, behavior, and the impact of the symptoms on the patient's ability to function. The CGIC is administered by an experienced clinician who is familiar with the disease under study and the likely progression of treatment. The clinician makes a judgment about the total picture of the patient at each visit: the severity of the illness, the patient's level of distress and other aspects of impairment, and the impact of the illness on functioning. The CGIC is rated without regard to the clinician's belief that any clinical changes are or are not due to medication and without consideration of the etiology of the symptoms.

The CGIC is a 7-point scale that requires the clinician to assess how much the patient's illness has changed relative to a baseline state at the beginning of the intervention and is rated as follows: 1, very much improved; 2, much improved; 3, minimally improved; 4, no change; 5, minimally worse; 6, much worse; or 7, very much worse.

CGIC should be assessed consistently by the same rater for each study participant. A separate CGIC assessment will be performed by the Investigator (Principal Investigator or Sub investigator) and caregiver.

Clinical Global Impression of Change (CGIC) for the physician and caregiver at Day 302 will be analyzed as an ordered categorical score and as a dichotomized response: "much improved" or "very much improved" versus other responses.

The proportion of subjects with each CGIC score and with the dichotomized response of either "much improved" or "very much improved" will be summarized by visit and treatment group.

The difference in CGIC dichotomized response rate between 50/28 mg Group and Control Group will be analyzed using a logistic regression model with terms for treatment group and disease duration. Participants who die or withdraw from the study, prior Day 302, will be counted as 'non responders'.

The odds ratio, its 95% CI and the p-value for 50/28 mg Group compared to the Control Group will be presented. The proportion of CGIC responders at other visits will also be analyzed in a similar way. In a situation where the model does not converge then exact logistic regression (Hirji, K. F. 2005) will be performed.

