# 2.1. Study Design

This 3-part study will evaluate the efficacy and safety of a higher dosing regimen of nusinersen in approximately 145 participants. The study will be conducted at approximately 65 sites globally. Following the completion of this study, all eligible participants may elect to enrol in a separate long-term extension study (232SM302), pending study approval by ethics committees and the appropriate regulatory authorities. In regard to participants rolling over from Part B, this will be done without unblinding the participant's treatment group.

Part B will consist of a pivotal, double-blind, active-controlled treatment period with either 2 or 4 loading doses of nusinersen (for the 50/28-mg Group and Control Group, respectively) administered intrathecally followed by maintenance doses approximately every 4 months thereafter. Approximately 75 participants with infantile-onset SMA and 24 participants with later-onset SMA will be randomized in a 1:2 ratio to receive either the currently approved dosing regimen or a 50/28-mg dosing regimen.

In the Control Group, up to a total of 8 participants will receive 4 loading doses of 12 mg of nusinersen administered intrathecally (Days 1, 15, 29, and 64), followed by maintenance doses of 12 mg on Days 183 and 279 (and a sham procedure on Day 135).

In the 50/28-mg Group, up to a total of 16 participants will receive 2 loading doses of 50 mg of nusinersen administered intrathecally (Days 1 and 15) and 2 sham procedures on Days 29 and 64, followed by maintenance doses of 28 mg on Days 135 and 279 (and a sham procedure on Day 183). In order to maintain blinding sham procedures will be used as shown in the table below.

Arm	Dose 1	Dose 2	Dose 3	Dose 4	Dose 5	Dose 6	Dose 7
50/28-mg	D1	D15	D29	D64	D135	D183	D279
Group	(50 mg)	(50 mg)	(sham)	(sham)	(28 mg)	(sham)	(28 mg)
Control (12/12	D1	D15	D29	D64	D135	D183	D279
mg)	(12 mg)	(12 mg)	(12 mg)	(12 mg)	(sham)	(12 mg)	(12 mg)
Group							

Randomization in Part B will be performed using interactive response technology (IRT).

Product: Nusinersen	Statistical Analysis Plan
Study: 232SM203	Version: 1.0

For Part B later-onset participants, the randomization will be stratified by age at informed consent as follows:

< 6 years and

 $\geq$  6 years

Blinded safety data will be reviewed on an ongoing basis by the Sponsor and the Medical Monitor. Unblinded safety data will be reviewed on an ongoing basis by an Independent Data Monitoring Committee (IDMC).

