#### 2.2. Sample Size Considerations

The sample size for Later-onset SMA in Part B is not based on statistical considerations.

A total of 24 participants with later-onset SMA will be randomized to the Control Group and 50/28-mg Group in Part B in a ratio of 1:2; this will allow the exploration of the safety, tolerability, **and efficacy** of the 50/28-mg dose of nusinersen in this population. If any participants with later-onset SMA enrolled in Part B do not complete the Day 183 dose and assessments (e.g., due to withdrawal) as a result of a public health or humanitarian emergency, up to 4 additional participants may be enrolled at the Sponsor's discretion.

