# 3. Definitions

### 3.1. Dates and Points of Reference

- Study Day 1: the date of the first dose of study treatment in 232SM203
- Study Day
  - $\circ \quad \mbox{For a date on or after Study Day 1}$

Study Day = (Date of Interest) - (Study Day 1) + 1

• For a date before Study Day 1

Study Day = (Date of Interest) – (Study Day 1)

In order to distinguish nominal visit names from duration defined in days, visit names will be referred to as "Day 15", "Day 29", etc., and "15 days" or "29 days", etc. will be used to define time intervals.

Overall time on study will be defined as the total number of days a participant is known to be followed on study calculated as follows:

Overall time on Study = (Last date on study) – (Date of first dose) +1

Last date on study is defined as the date of the latest visit or evaluation or telephone contact, or time of death from all available data for a given participant.

Disease duration is defined as time from age at symptom onset to age at informed consent.

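### The later-onset CGIC fallback to exact logistic regression conditions on disease duration with no stated unit or category, so in sparse data the recording unit alone can force p = 1

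*SAP*

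**What the plan says.** Part B later-onset SAP, section 5.1.7, compares the two arms on the proportion rated much or very much improved. It uses a "logistic regression model with terms for treatment group and disease duration", for physician and caregiver ratings at Day 302 and in a similar way at other visits. The outputs are fixed: "The odds ratio, its 95% CI and the p-value for 50/28 mg Group compared to the Control Group will be presented". The fallback is: "In a situation where the model does not converge then exact logistic regression".

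Section 3.1 of the same SAP gives the covariate: "Disease duration is defined as time from age at symptom onset to age at informed consent". It states no unit, rounding or cut-point. The split at 12 weeks belongs to the infantile-onset SAP. The only later-onset randomisation stratum is age below 6 years versus 6 years or older, and it is not in this model.

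The groups are small (section 2.1): "In the 50/28-mg Group, up to a total of 16 participants" and "In the Control Group, up to a total of 8 participants".

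**The concern.** Exact logistic regression tests treatment conditionally on the sufficient statistics of the other terms. Here these are the number of responders and the sum of disease duration over responders. The reference distribution is the list of all responder sets of the same size with exactly the same duration sum. If duration is recorded finely, few or no other sets match. With one matching set, p = 1 and the interval for the odds ratio is uninformative, whatever the arms show.

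The fallback is called when the ordinary fit fails, typically because one arm has no responders or no non-responders. Those are often the data sets with few responders or few non-responders, where the list of matching sets is shortest. A prespecified p-value would then rest on a recording unit that the SAP never fixes.

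**Working it through.** **Inputs.** From the SAP: 16 v 8 children, terms treatment and disease duration. Assumed: duration = age (uniform, 2 to 10 years, the per-protocol age limits) minus onset (about 6 to 18 months; the SAP gives only onset after 6 months). Two-sided p = 2 × the smaller tail. The SAP states no CGIC figure to reproduce.

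**Why the unit matters.** The SD of duration is √(8²/12 + 1²/12) = 2.33 years, about 850 days. For k responders among 24, the duration sum has SD about 850 × √(k(24−k)/23) days, spread over C(24,k) possible sets. The number of sets sharing a typical whole-day sum is about C(24,k)/(SD × 2.507):

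- k = 4: 10,626/(1,585 × 2.507) = 2.7
- k = 8: 735,471/(2,005 × 2.507) = 146

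In whole months each figure is about 30 times larger. Unrounded, no other set matches.

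**Enumeration, k of 16 responders v 0 of 8.** Unrounded duration gave one outcome and p = 1 in every simulated set at every k tried from 2 to 12. At 12/16 v 0/8 Fisher's p is 0.0013. For rounded duration:

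| k | Fisher p | Days: median set | Days: p = 1 | Months: p = 1 |
|---|---|---|---|---|
| 3 | 0.53 | 1 | nearly all | about 20% |
| 4 | 0.26 | 3 | 55-72% | 2-5% |
| 5 | 0.13 | 6.5 | 17% | 0% |
| 6 | 0.066 | 24 | 2% | 0% |
| 8 | 0.022 | 118 | 0% | 0% |
| 10 | 0.0064 | 311 | 0% | 0% |

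The range at k = 4 is the spread over repeated simulations. The simulated sets agree with the hand calculation.

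**Where the set is not degenerate.** The p-value follows the effect. At 10/16 v 0/8 the median p is 0.018 in days and 0.011 in months. It is still larger than Fisher's: at 7/16 v 0/8, about 0.11 in days and 0.076 in months, against 0.054. Part of that gap is convention, because doubling Fisher's smaller tail gives 2 × C(16,7)/C(24,7) = 2 × 11,440/346,104 = 0.066.

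**Few non-responders count equally.** Total duration is fixed, so conditioning on the sum over responders is the same as conditioning on the sum over non-responders. Take 16/16 v 4/8: Fisher's p is C(8,4)/C(24,4) = 70/10,626 = 0.0066. A whole-day reference set of about 3 outcomes cannot give a tail below 1/3. With true rates of 90% v 40%, separation occurred in about 20% of trials. Among those, p < 0.05 was reached in 0% with duration to 1/16 day, 17% in whole days and 70% in whole months.

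**How often it is triggered.** Non-convergence was taken as complete or quasi-complete separation. It occurred in about 40-70% of simulated trials at control rates of 5-10%. At higher control rates it was 16% (40% v 20%), 8% (40% v 30%), 6% (60% v 30%) and 2% (60% v 40%).

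**Both steps together, whole days.** At 30% v 10%, separation in 43.8% × p = 1 in 39% of those = 17% of trials. At 60% v 10%, 40.3% × 0% = 0%.

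**The case against.** The strongest reply is that 24 children and a time covariate do not by themselves make the test degenerate. That stands. A reader might infer that the fallback returns p = 1 whatever the treatment effect. The SAP does not support this, because it does not say that duration is carried unrounded, and in whole days or months with more than a handful of responders the test tracks the effect.

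A reader might also infer that separation is likely. The SAP gives no CGIC response rate, and the controls receive active nusinersen at the approved dose. The high trigger rates depend on assuming 5-10% control response.

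Third, a reader might infer that the CGIC analysis would then yield nothing. It would not be so: section 5.1.7 also analyses CGIC as an ordered score and summarises every category by visit and arm.

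It can further be said that, in whole days, p = 1 arises mainly at 4 or fewer responders, where Fisher's p is already 0.26 or more, so little is lost. That is fair for few responders. It fails for few non-responders, as 16/16 v 4/8 shows, and for duration finer than a day.

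Finally, this is a fallback for one secondary endpoint in a population whose size is not based on statistical considerations. That limits the reach of the point but does not make the rule sound.

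**Conclusion.** The point holds in limited form. As written, the fallback can return p = 1 and an uninformative interval because of how duration is recorded. This is certain in practice for unrounded duration, usual in whole days at 4 or fewer responders (or non-responders), and uncommon in whole months from 4 upward. Where it does not collapse, it is somewhat conservative.

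The sizes rest on the assumed age and onset distributions, assumed response rates, 24 children as planned, and separation as the meaning of non-convergence. The mechanism rests on none of these, only on the model terms and the uncategorised definition of duration. The change is worth making because it is nearly free, but no main conclusion of the study depends on it.

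**What to change.** In section 5.1.7 of the later-onset SAP, replace the fallback: if the model does not converge or shows complete or quasi-complete separation, fit Firth's penalised-likelihood logistic regression with the same terms and report profile-likelihood confidence intervals.

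Alternatively, keep the exact method but condition only on a categorical factor, such as the existing age stratum (below 6 years, 6 years or older) or a prespecified duration category, never on a continuous time. As a check, a median split of duration gave reference sets of 2,640 outcomes at 4/16 v 0/8 and 174,240 at 8/16 v 0/8. The median p-values were 0.35 and 0.040, close to Fisher's doubled tails of 2 × 1,820/10,626 = 0.34 and 2 × 12,870/735,471 = 0.035.

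The cost is one SAP sentence and a SAS option, with no extra data or participants. The downsides are small: Firth's method is not exact, and a category adjusts for duration more coarsely.

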# 5.1.8. Number of Serious Respiratory Events

All adverse events that are coded into the System Organ Class (SOC) of respiratory, thoracic, and mediastinal disorders, either as their primary SOC will be considered respiratory events. Only those classified as serious will be analyzed. By utilizing the above approach, rare occurrence of serious respiratory events in the Infection and Infestation SOC and Investigation SOC (if any) may not be included. However, a detailed review of the AE listing will be conducted to identify such events.

The number of serious respiratory events during the study will be analyzed using the rate at which they occur. For descriptive purposes, the aggregate rate will be calculated for each group by dividing the total number of serious respiratory events that occurred in the group by the total number of subject-years on study.

Product: Nusinersen	Statistical Analysis Plan
Study: 232SM203	Version: 1.0

Annualized serious respiratory event rate will be calculated for each subject as the number of serious respiratory events that the subject experienced divided by the number of days on study and this ratio multiplied by 365.

No formal statistical comparison is planned.

#### 5.1.9. Ventilator Use

The participant's ventilator use and respiratory aids will be collected at every study visit. If ventilation is used daily, the average number of hours per day for the past 7 days will be recorded.

[figure not shown]
The ventilation use will be summarized by visit and listed.

# 5.1.10. Change in the Parent Assessment of Swallowing Ability Scale (PASA)

Parent Assessment of Swallowing Ability (PASA) will be assessed using the PASA questionnaire. Caregivers will be asked a series of questions regarding the mealtime behavior of the participant.

The PASA questionnaire was developed by a Biogen team in order to assess the signs and symptoms of dysphagia. This questionnaire consists of 33 items across 4 domains that cover general feeding, drinking liquids, eating solid foods, and assessment of swallowing concerns. The first 3 of these domains are generally assessed with 5 levels of response (Never, Rarely, Sometimes, Often, and Always), although 2 items are assessed with a simple "Yes"/"No" answer. In the final domain, the assessment of swallowing concerns has 4 levels of response: Strongly Agree, Agree, Disagree, and Strongly Disagree. In answering each item, the caregiver is directed to consider the previous 7 days.

The number, mean score, and percentage of subjects scoring each category in the PASA Section 1 -General Feeding will be presented by visit. In addition, a stacked bar chart will be used to summarize the proportion of subjects in each category over time for each item. Depending on the number of subjects who complete PASA Sections 1,2, 3, and 4, similar presentations may also be made or alternatively the results from these visits will be listed.

Product: Nusinersen	Statistical Analysis Plan
Study: 232SM203	Version: 1.0

